3.0 SELECTION AND ENROLLMENT OF PARTICIPANTS

3.1 Inclusion Criteria

- 3.1.1 Ability of participant to provide informed consent.
- 3.1.2 Age 18 or older.
- 3.1.3 HIV-1 infection documented by any FDA licensed clinical test including HIV enzyme/antigen test or chemiluminescence immunoassay (E/CIA) or plasma

HIV-1 RNA viral load.

- 3.1.4 A diagnosis of HIV sensory neuropathy determined by a neurological exam performed by a nurse and defined per previous criteria^{7, 59} as one or more clinical signs, including diminished or dull/sharp sensation in feet or reduced ankle reflexes.
- 3.1.5 Current use of cannabis
- 3.1.6 Ability to describe THC and CBD content in cannabis products
- 3.1.7 Ability to respond to text messages

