
SCHEMA

Effect of Cannabis Administration and Endocannabinoids on HIV Neuropathic Pain

DESIGN: Our objective is to assess PLWH who have neuropathic pain and are currently using cannabis, including light use (1-4 times per month) and heavy use (5+ times per month). These participants will be enrolled in a study that consists of two stages: Stage 1) PLWH will participate in a 6-month mHealth text messaging program (Individual Monitoring of Pain and Cannabis Taken, or IMPACT) that will examine the association between cannabis obtained from local dispensaries and changes in daily pain. Participants will return for a visit after 6 months for follow-up testing so we can examine longitudinal changes in neuropathic pain, neuropsychological performance and EC function. Stage 2) A double blind crossover study where we administer three different doses of vaporized cannabis to each participant that contain THC and varying concentrations of CBD (low, medium, high), including: a) 2 vials of 0.01% CBD + 1.9% THC, b) 1 vial of 0.01% CBD + 1.9% THC and 1 vial of 5.1% CBD + 1.4% THC, and c) 2 vials of 5.1% CBD + 1.4% THC. Here we will examine the acute effects of cannabis obtained from NIDA on pain intensity, blood endocannabinoid (EC) levels, and the relationship of pain with heart rate variability (HRV).

POPULATION: PLWH with neuropathic pain and current cannabis use.

STRATIFICATION: none

REGIMEN OR INTERVENTION

Three doses of cannabis (with varying concentrations of CBD) administered once per day on three separate days.

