1.1 Background

HIV-related neuropathic pain (HIV-NP) represents a significant problem for PLWH. HIV sensory neuropathy (HIV-SN), typically characterized by sensory deficits, numbness, tingling, or pain in feet or hands, is a common health concern in people living with HIV (PLWH)¹. HIV-SN is often associated with neuropathic pain (NP) described as “stabbing”, “burning” or “aching” that is the most frequent source of HIV-SN disability², while the prevalence of reported pain in PLWH ranges from 27 to 97%³. A large scale study by our group indicated that 57% (881 out of 1539 PLWH) exhibited HIV-SN and 38% reported HIV-NP⁴. Treatment of HIV-NP remains difficult; a 2010 review indicated that only capsaicin, human nerve growth factor, and smoked cannabis showed superior pain reduction compared to placebo⁵. Studies at the University of California Center for Medicinal Cannabis Research (CMCR) indicate that 34-40% of patients exposed to cannabis cigarettes with delta-9-tetrahydrocannabinol (THC) exhibited significant pain reduction compared to 17-20% on placebo⁶⁻⁸. While THC doses in the 1.3% to 3.5% range alleviate pain for some participants, higher doses of THC (7-8%) did not provide additional benefit for pain reduction⁸ or actually increased capsaicin-induced pain in healthy volunteers⁹. Importantly, combined cannabidiol (CBD)/THC extracts are reported to be more effective at treating pain compared to THC alone in human cancer-related pain and in rodents^{10, 11}. CBD exhibits antioxidant and neuroprotective properties, inhibiting the release of inflammatory cytokines such as TNF α ¹². However, the optimal THC/CBD ratio for effective pain treatment is not yet known. There may also be discrepancies between data obtained from controlled clinical trials and the use of unregulated cannabis obtained from dispensaries. There is thus a clear need to close the gap between existing clinical data and real-life cannabis use from public sources, including the effects on the endocannabinoid (EC) system and NP.

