2.0 STUDY DESIGN

Our objective is to assess 100 community-dwelling PLWH with neuropathic pain (PLWH-NP) who are recruited and tested at the HIV Neurobehavioral Research Program (HNRP)/Center for Medicinal Cannabis Research (CMCR) facilities located at the UCSD Medical Center. These participants will be enrolled in a study that consists of two stages: 1) administration of three different doses of vaporized cannabis obtained from NIDA (one dose per day on three separate days) that contain THC and varying concentrations of CBD, including: a) 2 vials of 0.01% CBD + 1.9% THC, b) 1 vial of 0.01% CBD + 1.9% THC and 1 vial of 5.1% CBD + 1.4% THC, and c) 2 vials of 5.1% CBD + 1.4% THC; 2) participation in a 6-month text message monitoring study, the Individual Monitoring of Pain and Cannabis Taken (IMPACT), where pain and cannabis use from local dispensaries is tracked. We will use a randomized crossover design where all participants receive each of the three cannabis doses at the HNRP and then are subsequently enrolled into IMPACT. We will recruit individuals who are currently using cannabis at least once a month to treat pain. The primary outcome measures of the study will examine: 1) the acute effects of NIDA-obtained cannabis on pain, EC levels, and the relationship with HRV (Aim 1); 2) the association between dispensary-obtained cannabis and changes in pain reported via IMPACT (Aim 2); 3) the effect of chronic THC and CBD exposure on longitudinal changes in pain, EC measures, and neurocognitive performance (Aim 3). Secondary and exploratory analyses will compare NIDA-obtained and dispensary-obtained cannabis effects on neuropathic pain and evaluate if there are different effects of reported cannabis strain (Sativa, Indica), specific cannabis products (e.g., OG Kush, Sour Lemon, etc.), or mode (smoking, vaporizing, ingesting food product) on pre-post drug exposure changes in pain

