4.2 Cannabis Administration Protocol

Participants will receive vaporized cannabis using Volcano vaporizers (Storz and Bickel) with the aforementioned concentrations of CBD and THC at each of three visits. Allocation assignment of visits will be assigned using randomization schedule prepared by our statistician. The allocation schedule will be kept in the pharmacy and concealed from other study personnel. The cannabis will be stored in a freezer at 20°C until the day before use. At least 12 hours before each session, 800 mg of study cannabis will be thawed. The vaporization session will be performed in a HNRP negative pressure room designed to prevent the vapor from being transferred to rooms in which other occupants of the building are working. Puffs from the vaporizer balloon will be standardized so that a consistent amount is inhaled. This will be done according to a cued-smoking procedure shown to produce reliable increases in plasma THC levels⁶⁵. A nurse will provide instructions to participants to 'inhale' (5 seconds), 'hold smoke in lungs' (10 seconds), and 'exhale' and to wait before repeating the puff cycle (40 seconds). Each participant will inhale 4 puffs at each session, an amount that was well tolerated during our previous human laboratory experiments⁶⁰. We will measure vital signs (heart rate, respiration), pain intensity measured by a 0 to 10 numerical rating scale, and HRV at baseline (30 minutes before cannabis administration), at time zero (immediately after cannabis administration), and at 60, 120, and 180 minutes after drug administration. As a secondary measure of pain relief, we will use the Patient Global Impression of Change (PGIC) that will be measured hourly following administration of study medications. We will also conduct a von Frey assessment. The von Frey tool consists of monofilaments that are applied to the skin until bending of the filament occurs, calibrated to a specific pressure and designed to minimize movement artifacts⁶⁶. Increased pain to von Frey stimulation occurs in NP and clinical trials indicate that cannabis treatment can reduce allodynia on this test⁶⁷. We will include this measure in our battery and assess pain using the VAS as previously reported⁶⁷; the von Frey filament will be applied on the dorsum of the more painful foot until bending is observed for 3 seconds, followed by a VAS pain rating.

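### The inclusion criteria in Section 3.1 do not enforce the stated population: they require a sign of neuropathy and cannabis use, but neither neuropathic pain nor use of cannabis to treat pain

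*Combined protocol and SAP*

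**What the plan says.** Three places state the intended population. The abstract describes 100 people with HIV whose cannabis use is for neuropathic pain. The Schema gives "POPULATION: PLWH with neuropathic pain and current cannabis use". Section 2.0 opens with "Our objective is to assess 100 community-dwelling PLWH with neuropathic pain (PLWH-NP" and adds "We will recruit individuals who are currently using cannabis at least once a month to treat pain".

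Section 3.1 lists seven inclusion criteria. The two that bear on this point are 3.1.4, a diagnosis of HIV sensory neuropathy defined as "one or more clinical signs, including diminished or dull/sharp sensation in feet or reduced ankle reflexes", and 3.1.5, "Current use of cannabis". The other five cover consent, age, documented HIV-1 infection, ability to describe THC and CBD content, and ability to respond to text messages. None of the seven, and none of the exclusions in Section 3.2, refers to pain. No minimum pain score appears anywhere.

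The acute outcome is "pain intensity measured by a 0 to 10 numerical rating scale" (Section 4.2), taken 30 minutes before each dose and repeatedly afterwards. Section 7.1 compares doses on this scale with a mixed model, compares the proportions with a 30% reduction by chi-square test, and derives a number needed to treat. Section 7.4 bases the Aim 1 power on the change from baseline in pain.

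**The concern.** Someone with one reduced reflex, no pain and any current cannabis use meets 3.1 as written but is outside the population that the rest of the protocol describes. The background shows this is not a remote combination. It reports "57% (881 out of 1539 PLWH) exhibited HIV-SN and 38% reported HIV-NP", so on either reading of the 38% many people with neuropathy have no neuropathic pain.

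Two things are at stake:

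- **Dilution.** A participant at 0 on the pain scale cannot improve on it and so contributes no dose effect to the average.
- **An undefined outcome.** A 30% reduction from 0 has no value, and Section 7.1 does not say whether such a session counts as a non-response, is dropped, or is handled in some other way. The response proportions and the number needed to treat both depend on that choice.

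**Working it through.** **Step 1: the texts side by side.**

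| Element | Abstract, Schema, 2.0 | 3.1 and 3.2 |
|---|---|---|
| Neuropathic pain | Stated in all three | Absent; one neuropathy sign suffices |
| Cannabis used for pain | Stated in the abstract and 2.0 | Absent; current use suffices |
| At least monthly use | Stated in 2.0 | Absent |
| Minimum pain score | Absent | Absent |

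**Step 2: does neuropathy imply pain?** The inputs are the 1539, 881 and 38% of Section 1.1. If the 38% is of the whole cohort, 0.38 × 1539 = 585 people have pain. Even if all of them are among the 881, 585/881 = 66% have pain and 34% do not. If the 38% is of the 881, 62% have no pain. These shares describe a general HIV cohort, not people recruited because they treat pain with cannabis.

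**Step 3: reproduce the stated power.** From Section 7.4, n = 100, three doses and f = 0.180; from Section 7.1, alpha = 0.05. The repeated-measures F test has noncentrality λ = f² × n × 3/(1 − ρ) on 2 and 198 degrees of freedom, where ρ is the within-person correlation, which the plan does not state.

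- ρ = 0: λ = 0.0324 × 300 = 9.72, power 79.7%. A one-way calculation with N = 300 gives 79.9%.
- ρ = 0.25: λ = 9.72/0.75 = 12.96, power 90.3%.
- ρ = 0.5: λ = 9.72/0.5 = 19.44, power 98.1%.

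The stated 80% therefore corresponds to ρ = 0.

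**Step 4: dilution.** Assume f = 0.18 is the effect among those with pain, and that a share q has no pain and no dose effect. The mean contrast shrinks by (1 − q).

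- Case A: pain-free participants also add no variance, so the effect becomes f√(1 − q) and λ is multiplied by (1 − q).
- Case B: they add the same variance as others, so the effect becomes f(1 − q) and λ is multiplied by (1 − q)².

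For example, at q = 20% and ρ = 0, λ is 9.72 × 0.8 = 7.78 in case A (power 69.7%) and 9.72 × 0.64 = 6.22 in case B (power 59.4%).

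Power, case B to case A:

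| Assumed share pain-free | ρ = 0 | ρ = 0.25 | ρ = 0.5 |
|---|---|---|---|
| 0% | 80% | 90% | 98% |
| 5% | 75-77% | 87-89% | 97-98% |
| 10% | 70-75% | 83-87% | 95-97% |
| 20% | 59-70% | 73-82% | 89-95% |

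A simulation with 4000 runs per cell at ρ = 0 agrees: 70-74% at q = 10% and 59-69% at q = 20%.

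**Step 5: the responder outcome.** Percentage reduction is (baseline − follow-up)/baseline, which is undefined at baseline 0. Because baseline is taken before each session, this can occur even in someone who had pain at screening.

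**The case against.** The strongest reply is that the protocol states its intent plainly: neuropathic pain is named in the abstract, the Schema and the first sentence of Section 2.0, and 2.0 limits recruitment to people using cannabis for pain. That stands, and it narrows the practical risk. A reader might infer from 3.1 that the trial was designed to admit pain-free people. The documents do not support that. The defect is that the list of criteria omits a restriction made elsewhere. Nor do the documents say that screening would rely on 3.1 alone.

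A reader might also apply the background shares directly and conclude that power falls to about 0.61 (34% pain-free) or 0.38 (62% pain-free). Those figures are the case A results at ρ = 0, but the shares come from an unselected cohort and the 62% rests on an unresolved denominator. Section 7.4 also gives a detectable effect rather than an expected one, and says that the mixed model will have higher power. Actual power may therefore stay above 80% with some pain-free participants.

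The floor is also narrower than it may look. A score of 1 can still fall to 0. Von Frey-evoked pain may respond in someone with little spontaneous pain. The endocannabinoid and heart-rate-variability outcomes have no pain floor.

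None of this closes the gap. Recruitment for pain in general is not recruitment for neuropathic pain, and the criteria that define eligibility contain neither.

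**Conclusion.** The concern holds as an inconsistency: Section 3.1 admits people whom the abstract, the Schema and Section 2.0 exclude. This rests on the text alone. One figure after Section 3.2 is not available and could not be checked.

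The direction of the effect on the pain contrast is clear, but its size is not known. It depends on the pain-free share among those enrolled, on the within-person correlation, and on reading f = 0.18 as the effect in those with pain; the documents settle none of these. With 10 to 20% pain-free, power lies between 59% and 75% at zero correlation and between 89% and 97% at a correlation of 0.5. A flat statement that the trial is underpowered would go too far.

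A reader might also infer that a particular minimum pain score is needed. The documents give no basis for one, and whether to set one is a design choice. A screening minimum would not by itself resolve a session baseline of 0. The missing rule for that case is a separate gap in Section 7.1. The point is worth correcting because the correction is small and the population is already stated.

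**What to change.** 1. Reconcile Section 3.1 with the abstract, the Schema and Section 2.0. Add current neuropathic pain as an inclusion criterion, and extend 3.1.5 so that it carries the Section 2.0 recruitment rule of at least monthly cannabis use for pain. Leave the question of a minimum score to the sponsor.
2. State in Section 7.1 how a session with a baseline score of 0 is handled in the 30% responder comparison and in the number needed to treat.

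The cost is an amendment of one or two eligibility lines and one analysis sentence. The pain scale is already collected. The recruitment pool becomes somewhat smaller, by an amount that the documents do not allow one to estimate, but it is drawn from the population that the protocol already says it studies.

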3.2 Exclusion Criteria

- 3.2.1 Meeting criteria for current alcohol or substance dependence
- 3.2.2 Traumatic brain injury
- 3.2.3 Dementia or Alzheimer's disease
- 3.2.4 Psychosis
- 3.2.5 A respiratory condition, i.e., pulmonary disease, that would be exacerbated by inhaling vaporized cannabis.
- 3.2.6 History of cardiovascular disease, including myocardial infarction or stroke
- 3.2.7 Uncontrolled hypertension, defined as a systolic blood pressure greater than 150 mm Hg or a diastolic blood pressure greater than 100 mm Hg.
- 3.2.8 Pregnancy, breastfeeding, or unwillingness to prevent pregnancy during the cannabis administration portion of the study (using birth control in female participants of child-bearing age).
- 3.2.9 Unwillingness or inability to receive or respond to text messages.

[figure not shown]
4.0 STUDY TREATMENT

4.1 NIDA Drug Supply Provision of Cannabis Product

We will be administering three cannabis doses to each participant using the vaporizer, including varying concentrations of CBD (low, medium, high): a) 2 vials of 0.01% CBD + 1.9% THC, b) 1 vial of 0.01% CBD + 1.9% THC and 1 vial of 5.1% CBD + 1.4% THC, and c) 2 vials of 5.1% CBD + 1.4% THC.

4.2 Cannabis Administration Protocol

Participants will receive vaporized cannabis using Volcano vaporizers (Storz and Bickel) with the aforementioned concentrations of CBD and THC at each of three visits. Allocation assignment of visits will be assigned using randomization schedule prepared by our statistician. The allocation schedule will be kept in the pharmacy and concealed from other study personnel. The cannabis will be stored in a freezer at 20°C until the day before use. At least 12 hours before each session, 800 mg of study cannabis will be thawed. The vaporization session will be performed in a HNRP negative pressure room designed to prevent the vapor from being transferred to rooms in which other occupants of the building are working. Puffs from the vaporizer balloon will be standardized so that a consistent amount is inhaled. This will be done according to a cued-smoking procedure shown to produce reliable increases in plasma THC levels⁶⁵. A nurse will provide instructions to participants to 'inhale' (5 seconds), 'hold smoke in lungs' (10 seconds), and 'exhale' and to wait before repeating the puff cycle (40 seconds). Each participant will inhale 4 puffs at each session, an amount that was well tolerated during our previous human laboratory experiments⁶⁰. We will measure vital signs (heart rate, respiration), pain intensity measured by a 0 to 10 numerical rating scale, and HRV at baseline (30 minutes before cannabis administration), at time zero (immediately after cannabis administration), and at 60, 120, and 180 minutes after drug administration. As a secondary measure of pain relief, we will use the Patient Global Impression of Change (PGIC) that will be measured hourly following administration of study medications. We will also conduct a von Frey assessment. The von Frey tool consists of monofilaments that are applied to the skin until bending of the filament occurs, calibrated to a specific pressure and designed to minimize movement artifacts⁶⁶. Increased pain to von Frey stimulation occurs in NP and clinical trials indicate that cannabis treatment can reduce allodynia on this test⁶⁷. We will include this measure in our battery and assess pain using the VAS as previously reported⁶⁷; the von Frey filament will be applied on the dorsum of the more painful foot until bending is observed for 3 seconds, followed by a VAS pain rating.

To assess participant perception of drug effects, the Marijuana subscale (M-scale) of the Addiction Research Center Inventory (ARCI) will be administered⁶⁸. The M-scale has 12 true/false statements describing the subjective effects of marijuana (see attached ARCI Marijuana subscale). We have elected not to include a placebo in the current design because participants with prior cannabis use are likely to be aware they are not receiving the drug, given the lack of psychoactive/physiological effects, and this may confound their report of pain. We have also chosen to administer one fixed dose (8 puffs) to all participants to avoid the confound of varying levels of drug intake. Participants will be allowed to engage in normal activities, such as reading or listening to music between assessments. Participants will remain in the laboratory under direct observation by nursing staff for 3.5 hours after the vaporization inhalations are completed (30 minutes after the 180-minute sample collection). At that time a final vital sign status check will be made and upon satisfactory readings, the subject will be released and driven back to his/her domicile by taxicab or prearranged transportation.

4.3. IMPACT

All participants will be instructed on how to use the IMPACT text messaging/website survey program, practice the SMS interface with study staff, and set up personalized preferences (e.g., optimal times to receive messages). If they do not have a cell phone capable of receiving and sending text and picture messages, one will be provided to them at the baseline session and we will purchase bulk 'minutes' in order to provide the text message intervention. Participants will also receive digital milligram scales that they can use to weigh out cannabis products, including joints, blunts, and bowls. Participants will not be required to use the scales, but they will be provided as an optional tool to improve the accuracy of reporting cannabis quantity. Participants will not be responsible should they lose or break the devices. We will also ask participants to identify the source of their cannabis products, including the name of the medical dispensary where the product was obtained. If the participant obtained cannabis from another source, such as a neighbor or friend, this source will be anonymously identified as "friend". We will not collect any names or any identifying information about any specific individuals who provide cannabis to the participant; only the names of medical dispensaries in San Diego will be collected. Participants will also not be required to disclose the source of the cannabis and may select an option of "decline to provide" or "I do not know" or "unknown" when asked about this information. (45 minutes). After the 6-month IMPACT is completed, participants will return for a visit that will include the same assessments during the pre-entry visit, including a medical exam with neuropathy testing, assessment of substance use, administration of pain rating scales, neurocognitive testing, and a blood draw to repeat baseline evaluations including THC, CBD, and EC biomarkers and check hepatic/renal function. We will not administer cannabis at this session, and similar to the pre-entry visit, request that participants abstain from cannabis for 24 hours before this visit.

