7.0 STATISTICAL ANALYSIS PLAN

7.1 Aim 1 Measures and Analyses

Data will be assessed for normality and transformations applied as needed (e.g., log). Neuropathic pain before and after acute cannabis administration will be assessed by NPRS and the von Frey test. Plasma AEA and 2-AG will be measured with LC/MS. Flow cytometry will quantify the percentage of PBMC that express CB2, FAAH, and MAGL, including monocytes, CD4+ T-cells, and CD8+ T-cells. To examine the effect of different CBD/THC products on NP and EC biomarkers, we will use a linear mixed model with subjects treated as a random effect to model the response measures. This methodology takes into account the repeated measures aspect of the within-subjects crossover study design, incorporating information from observations for each subject at different treatment doses and multiple time points within each dose. For initial modeling, terms will include dose (0.01%, 5.1% - 4 puffs, and 5.1% - 8 puffs) CBD treated as a categorical variable), time (0, 60, 120 and 180 minutes after exposure treated as a continuous variable), and dose x time interaction. Additional terms will also be included for the sequence in which the treatments were administered (e.g., low CBD vs. medium CBD) and for second-order time (time²). The quadratic term is intended to model a U-shaped response curve if responses initially increase (or decrease), reach a maximum (or minimum), then decrease (or increase) back to baseline levels. For each outcome measure, each of these last 2 terms will be omitted from subsequent models and not reported if nonsignificant. Any potential factors that associate with outcome variables at the $\alpha = 0.20$ level in single-predictor analyses (history of light vs. heavy cannabis use, mode of prior cannabis use – i.e., engaging in smoking, or vaporizing, or both), time since last cannabis use before baseline, duration of cannabis use over lifetime, presence of adolescent cannabis use, duration of HIV infection, nadir CD4, viral load, gender, the presence of other non-cannabis analgesic medications, history of non-cannabis substance use disorders) will be included in the linear model. Dose effects at each time point will be assessed with mixed modeling after re-coding time as a categorical factor and including dose and dose x time terms (plus a term for sequence if this is significant in the initial model). Differences among doses will be evaluated using the Tukey honestly significant difference (HSD) comparison tests for differences of effects over all time points and contrasts within each

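### The three dosing sessions have no stated abstinence request, recent-use check or interval beyond separate days, and the Aim 1 model only partly protects against own use and carry-over

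*Combined protocol and SAP*

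**What the plan says.** Section 4.3 describes the return visit after six months of text-message monitoring. Of that visit it says "We will not administer cannabis at this session", and that staff will, "similar to the pre-entry visit, request that participants abstain from cannabis for 24 hours before this visit". The request therefore covers the pre-entry visit and the six-month visit.

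Section 4.2 sets out the dosing sessions in detail: thawing ("At least 12 hours before each session, 800 mg of study cannabis will be thawed"), puff timing, measurement times and discharge. It contains no abstinence request, no question about recent use and no rule for a participant who arrives after using their own product.

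On spacing, section 2.0 says "one dose per day on three separate days" and the Schema says "Three doses of cannabis (with varying concentrations of CBD) administered once per day on three separate days". Neither gives a minimum interval. The design is within-person ("We will use a randomized crossover design where all participants receive each of the three cannabis doses") in active users ("We will recruit individuals who are currently using cannabis at least once a month to treat pain").

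Section 7.1 models the response with dose, time at 0, 60, 120 and 180 minutes, and their interaction. Terms for treatment sequence and squared time are added, and each is removed if nonsignificant. One candidate covariate is "time since last cannabis use before baseline", kept only if it is associated with the outcome at the 0.20 level.

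**The concern.** Aim 1 is a within-person comparison of three acute doses. Section 4.2 justifies a single fixed dose by the wish to keep drug intake from varying between participants. Own use shortly before a session, or a study dose the day before, brings that variation back. It can alter the pre-dose pain score, the circulating THC and CBD, and the endocannabinoid baseline at that session.

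Two different harms are possible. Own use that differs between one person's three sessions adds session-to-session noise to the dose contrasts. Residual effect from the previous study dose can bias those contrasts. The 30% responder rates and number needed to treat in section 7.1, and the laboratory-versus-dispensary comparison in section 7.2, depend on the same pre-dose pain. Section 3.1 sets no minimum pain score, so a lowered pre-dose rating would not be screened out.

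**Working it through.** **1. The plan's own figure.** Section 7.4 gives n = 100, three doses, Cohen's f = 0.180 and 80% power. For a repeated-measures F test, λ = f²·n·3/(1 − ρ). With ρ = 0, λ = 0.0324 × 300 = 9.72 on 2 and 198 degrees of freedom, and power is 79.7%. The stated d range also reproduces (0.180 × 6/√8 = 0.382; 0.180 × √6 = 0.441), as does pairwise power at 0.05/3 (0.613 to 0.759). The stated figures thus imply a between-session correlation near 0; at ρ = 0.5 power would be 98.1%. They contain no allowance for own use or carry-over.

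**2. How often own use precedes a session.** Section 7.4 (Aim 2) assumes 2 uses per week. Assume Poisson use, the same rate for everyone, unrelated to session timing, and applicable to the dosing period.

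- One session: 1 − exp(−2/7) = 25%.
- At least one of three: 1 − exp(−6/7) = 58%.
- At the Schema's use bands, per session: about 3% at 1 per month, 12% at 4 per month, 15% at 5 per month.

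The Schema places the monitoring stage before the crossover and section 2.0 places it after, so the background use at the dosing sessions is itself unsettled.

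**3. Cost in precision.** If own use inflates the session-level variance by a fraction v, f becomes 0.180/√(1 + v). With ρ = 0:

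| v | f | Power |
|---|---|---|
| 0.10 | 0.172 | 76% |
| 0.25 | 0.161 | 70% |
| 0.50 | 0.147 | 61% |

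To place these values: if own use shifts a session's score by δ standard deviations with probability 0.25, the added variance is about 0.25 × 0.75 × δ² = 0.1875δ². Then v = 0.10 needs δ = √(0.10/0.1875) = 0.73, and v = 0.50 needs δ = 1.63. The last row is a severe case.

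**4. Carry-over.** Assume all six orders are used equally and a fraction q of the previous dose's effect persists. Two thirds of sessions have a predecessor, equally often each of the other two doses. On raw scores, high minus low becomes (H − L) + (2/3)·q·(L − H)/2 = (H − L)(1 − q/3). If the residue sits only in the pre-dose value and change scores are analysed, the sign reverses and the factor is 1 + q/3. If it affects pre-dose and post-dose values equally, it cancels in change scores.

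| q | Raw-score factor | Power | Baseline-only factor |
|---|---|---|---|
| 0.10 | 0.97 | 77% | 1.03 |
| 0.25 | 0.92 | 72% | 1.08 |
| 0.50 | 0.83 | 63% | 1.17 |

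Section 7.4 speaks of change from baseline, whereas the section 7.1 model lists only post-dose times and does not mention the pre-dose value. The text therefore does not settle which column applies.

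**5. What the safeguards do.** Random order balances carry-over across participants but does not remove it. A sequence effect, read as the order group, is a between-participant term: it does not estimate period effects or first-order carry-over, and it may be dropped. No period or carry-over term is named. The own-use covariate does not say which baseline it refers to, and it has to survive screening.

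**The case against.** The plan is not unprotected. The order is randomised and concealed in the pharmacy, pain and heart rate variability are measured half an hour before each dose, a sequence term enters the initial model, and recent own use and light or heavy use are candidate covariates. The quadratic time term anticipates a return towards baseline within the session, which suggests a small next-day q for pain. Current substance dependence is an exclusion. These points stand, and they limit the size of the problem.

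A reader might infer several stronger things that the documents do not support.

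- That sections 4.2 and 4.3 contradict each other. Section 4.3 concerns other visits and gives no reason for its request; section 4.2 is silent, which is an omission.
- That contamination must shrink the contrasts. Own use unrelated to a concealed order, with an additive effect, leaves the expected contrast unchanged. Attenuation needs a floor effect or an interaction, neither of which can be sized here. Carry-over can act in either direction.
- That the covariate is certainly one value per person. Section 4.2 uses baseline for the pre-dose reading and section 4.3 uses it for entry measurements, so a session-level meaning is possible.
- That one small own use swamps the study dose. The 800 mg thawed holds at most 800 × 1.9% = 15.2 mg THC, and 0.15 g of a product above 10% THC holds more than 15 mg. But the 0.15 g is an assumption, and neither figure is an absorbed dose, since the study delivers a fixed number of puffs.

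Finally, the pre-entry visit is not described elsewhere in the text, and a figure after section 3.2 is not shown. If that figure is a visit schedule, it may hold the missing rule.

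**Conclusion.** The point holds as a gap in the stated procedure and model. As written, the protocol permits unrecorded own use before a dosing session and dosing on consecutive days, within a crossover meant to isolate acute dose effects. The existing safeguards do not close this.

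About 25% of sessions and 58% of participants would be affected within a 24-hour window, given Poisson use at two per week unrelated to sessions. The likely consequence of own use is lost precision: 76% to 61% power in place of 80% for 10% to 50% extra variance. These figures are on the plan's implied zero correlation between sessions; with positive correlation the starting power is higher. Carry-over bias is 1 − q/3 or 1 + q/3, with q and the direction both undetermined by the documents. The conclusion is subject to the sponsor confirming that the unseen figure contains no abstinence or spacing rule.

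**What to change.** - **Protocol.** Reconcile section 4.2 with 4.3: state whether the pre-visit abstinence request applies to the dosing sessions, and what interval separates them. Both lengths are for the investigators to set.
- **Data.** At each dosing session, record the time, amount and product of the last own use.
- **Section 7.1.** Define the own-use covariate at session level, enter it in the Aim 1 model without the 0.20 screen, and add a period term.
- **Sensitivity.** Add a supportive analysis that excludes sessions with own use inside the requested window. The primary analysis should keep every observation, as the plan already intends, because exclusion discards post-randomisation data.

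The cost is a short amendment, one question per session and some SAP wording. Some sessions may need rescheduling, and heavy users may find a request harder to meet. Own use that is not recorded on the day cannot be reliably recovered later.
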